3.7.5.3 Physical Examination and Vital Signs

3.7.5.3.1 Physical Examination

A complete physical examination will be performed at screening, and a targeted physical examination to address any new concerns will be performed at all other visits indicated in the Schedule of Assessments ([Table 3.7-1](#)). A complete physical examination will include height (screening only), weight, waist circumference, and calculation of body mass index (BMI) (screening and Day 42/ET only); and assessment of the head, eyes, ears, nose, throat, thorax, abdomen, urogenital, skin and mucosae, neurological, and extremities. Examinations with abnormal results that are deemed clinically significant should be repeated to ensure reproducibility of the abnormality. Any abnormalities considered by the investigator to be clinically significant are to be recorded as AEs on the AE eCRF.

Protocol 405-201-00013

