3.7.1 Schedule of Assessments

3.7.1.1 Visit 1 (Screening)

The screening period begins after consent is obtained and will take place between Day -35 and Day -8 prior to the initiation of the single-blind placebo run-in period. Completion of screening activities may require more than 1 visit. All procedures outlined for screening in the Schedule of Assessments ([Table 3.7-1](#)) will be performed. The following should also be noted:

- The investigator or his/her designee must obtain informed consent from the subject prior to any trial-related procedures being performed.
- A urine drug screen will be collected and sent to the central lab for evaluation. If subjects are taking disallowed medications and they are able to taper appropriately and safely, they will do so during the screening period. If medication taken is for ADHD, a minimum of 7 days off stimulants and 21 days off nonstimulants will be required before the single-blind placebo run-in period. A complete washout schedule, including common excluded medications and herbal preparations, is provided in [Section 4.1](#). A subject who tested positive for any prohibited medications at the screening visit must have a repeat urine drug screen that is confirmed as negative prior to performing Visit 2.
- An assessment of all inclusion and exclusion criteria will be made to determine the subject's eligibility for the trial.
- Medical and psychiatric history will be recorded, including the DSM-5 diagnosis of ADHD using the ACDS Version 1.2.
- Subjects will be administered the ASRS.
- A urine pregnancy test will be performed for all females of childbearing potential (FOCBP). If the urine pregnancy test is positive, the result should be confirmed with a serum pregnancy test. Subjects with a positive serum test result will be excluded from the trial.

External quality oversight methods will be used by Clinical Surveillance & Training (CST) to promote appropriate subject enrollment. Such methods will require sites to communicate certain aspects of subject data during the screening period to CST as detailed in the Operations Manual. Subjects cannot be randomized until approval from CST has been received. The investigator is responsible for ensuring that subjects are eligible for enrollment into the trial and for assessing subject safety throughout the trial.

Protocol 405-201-00013

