3.7.5.3.2 Vital Signs

Vital signs including systolic blood pressure and diastolic blood pressure, heart rate, respiratory rate, and body temperature will be measured at the time points described in the Schedule of Assessments ([Table 3.7-1](#) and [Table 3.7-2](#)). Blood pressure and heart rate measurements will be made in the supine and standing positions after the subject has been in each position for at least 3 minutes. The supine measurements will be performed first followed by the standing measurements. Temperature and respiratory rate will be taken with the subject in the supine position.

Subjects should be monitored for potentially clinically significant vital signs values ([Appendix 3](#)). Abnormal results that are deemed clinically significant should be repeated to ensure reproducibility of the abnormality. Any abnormalities considered by the investigator to be clinically significant are to be recorded as AEs on the AE eCRF ([Section 5.2](#)).

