4.1 Prohibited Medications

Subjects who are currently taking any therapy for ADHD at screening will washout from their current ADHD therapy (see [Table 4.1-1](#)) before the start of the single-blind placebo run-in period (Day -7). All subjects must agree to discontinue all prohibited medications during the screening period. [Table 4.1-1](#) provides the required duration of washout for selected prohibited medications. All other prohibited medications must be discontinued at least 24 hours before Day -7.

Protocol 405-201-00013

Medication		Required Washout Prior to Start of Placebo Run-in Period
1.	Antidepressants Fluoxetine All other antidepressants	28 days 14 days
2.	Benzodiazepines	7 days
3.	Hypnotics, including non-benzodiazepine sleep aids	7 days
4.	ADHD medications Stimulants Nonstimulants	7 days 21 days
5.	Sedating antihistamines (eg, diphenhydramine, hydroxyzine, chlorpheniramine)	7 days
6.	Antihypertensives Clonidine Propranolol Guanfacine	21 days
7.	Anorexics (weight loss supplements)	7 days
8.	Investigational compounds	7 days

Table 4.1-2 lists all medications prohibited during the trial, including exceptions, where appropriate.

1.	All psychotropic agents including, but not limited to, the following: a) Antipsychotics, including depot formulations b) Anticonvulsants c) Antidepressants d) Mood stabilizers (ie, lithium) e) Benzodiazepines ^a f) Hypnotics g) All medications intended for the treatment or management of ADHD symptoms (on or off label use), including but not limited to any form of: amphetamine (mixed salts), atomoxetine, clonidine, dexamfetamine, guanfacine, lisdexamfetamine, and methylphenidate h) Opioid analgesics, unless permission is obtained from the medical monitor. Permission for opioid use may be considered for a documented and clinically appropriate indication (eg, episodic pain condition, tooth extraction) if prescribed at a medically appropriate dose and frequency. i) Nutritional supplements and non-prescription herbal preparations with central nervous system effects (eg, St. John's Wort, omega-3 fatty acids, melatonin, kava extracts, GABA supplements, etc) j) Sedating antihistamines (eg, diphenhydramine, hydroxyzine, chlorpheniramine)
2.	Investigational agents
3.	Barbiturates, except for the treatment of migraine headaches, provided that in the opinion of the investigator the dosing is medically appropriate.
4.	The following antihypertensive medications: propranolol, clonidine, guanfacine

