7.1 Baseline Definition

Baseline for the single-blind placebo run-in period refers to last available measurement prior to the start of administration of placebo in the single-blind placebo run-in period.

For analyses of the double-blind treatment period data, the baseline is defined as the last available measurement prior to the first dose of double-blind Investigational Medicinal Product (IMP) in the double-blind treatment period.

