9.5.1 Body Weight, Waist Circumference and Body Mass Index (BMI)

Analyses of body weight, waist circumference and BMI will be performed for the Safety Sample. The mean change from baseline of the double-blind treatment period to Day 42 (OC) and last visit in the double-blind treatment period in body weight will be tabulated and analyzed using ANCOVA. The ANCOVA models for both the OC and last visit analyses will

SAP 405-201-00013

include the baseline of the double-blind treatment period body weight and the treatment group.

Percentages of patients showing significant weight gain ($\geq 7\%$ increase in weight), as well as percentages of patients showing significant weight loss ($\geq 7\%$ decrease in weight) baseline of the double-blind treatment period to Day 42 (OC and LOCF) will be analyzed using Cochran-Mantel-Haenszel (CMH) General Association Test.

Body mass index is defined as weight in kilograms divided by the square of height in meters.

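### No body weight is scheduled between screening and the first double-blind dose, so the SAP's double-blind baseline weight is in practice a screening weight taken 8 to 35 days before Day 1

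*Protocol*

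**What the plan says.** **When weight is taken.** Protocol 3.7.5.3.1 lists, within the complete physical examination, "height (screening only), weight, waist circumference, and calculation of body mass index (BMI) (screening and Day 42/ET only"). After screening the examination is narrower: "a targeted physical examination to address any new concerns will be performed at all other visits indicated in the Schedule of Assessments". Table 3.7-1 marks a physical examination at screening, Day 21 and Day 42/ET, and has no separate row for weight. Vital signs are taken at Visits 2 and 3, but Protocol 3.7.5.3.2 does not name weight among them: "Vital signs including systolic blood pressure and diastolic blood pressure, heart rate, respiratory rate, and body temperature will be measured".

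**How weight is analysed.** For double-blind data, SAP 7.1 states that "the baseline is defined as the last available measurement prior to the first dose of double-blind Investigational Medicinal Product (IMP"). SAP 9.5.1 applies this to weight: "The mean change from baseline of the double-blind treatment period to Day 42 (OC) and last visit", using an ANCOVA with treatment and baseline weight. It also compares the proportions with a 7% or greater gain or loss by a CMH test. Protocol Appendix 3 and SAP Appendix 1 use the same 7% criteria.

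**What happens before dosing.** Under Protocol 3.7.1.1, screening "will take place between Day -35 and Day -8 prior to the initiation of the single-blind placebo run-in period". Washout sits inside it. Protocol 4.1 says "Subjects who are currently taking any therapy for ADHD at screening will washout from their current ADHD therapy", and Protocol 3.7.1.1 adds "a minimum of 7 days off stimulants and 21 days off nonstimulants will be required before the single-blind placebo run-in period". Table 4.1-1 gives 7 days for weight-loss supplements. Randomization is at Visit 3, and double-blind dosing starts the next day (Day 1).

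**The concern.** SAP 7.1 defines one baseline for the run-in and another for the double-blind period. For weight, both resolve to the same screening value, so a table headed as change from the double-blind baseline reports change from screening. It then includes whatever happened during washout and a week of placebo.

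Weight matters here. Protocol 1.3 names decreased appetite among the most common adverse events, and safety and tolerability are the secondary objective. At stake are each arm's mean change, the 7% gain and loss incidences, and the precision of the comparison. Waist circumference and BMI share the problem.

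The plan is stricter elsewhere. Vital signs and ECGs are repeated at Day -1. Under Protocol 3.7.5.2, baseline laboratory tests may be skipped only if a fasting screening sample is less than 14 days old. Weight has no repeat and no age limit.

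**Working it through.** **1. Reproduce the plan's own figure.** Protocol 3.7 gives a 28-day screening and washout period. Day -35 to Day -8 inclusive is 35 - 8 + 1 = 28 days, which agrees.

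**2. Age of the baseline weight.** There is no Day 0 (Day -1 is followed by Day 1), and Day 1 to Day 42 is 41 days.

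- Earliest weight, Day -35: 28 days to Day -7, 35 days to Day 1, and 35 + 41 = 76 days to Day 42. Pre-drug share 35/76 = 46%.
- Latest weight, Day -8: 1 day to Day -7, 8 days to Day 1, and 8 + 41 = 49 days to Day 42. Pre-drug share 8/49 = 16%.
- With a Day -1 weight: 1 day to Day 1. Share 1/42 = 2%.

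The low end does not describe someone weighed while still on ADHD medication. Seven days before Day -7 is Day -14, so a stimulant user's share is at least 14/(14 + 41) = 25%. Twenty-one days before Day -7 is Day -28, so a nonstimulant user's is at least 28/(28 + 41) = 41%.

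**3. Effect on mean change.** Let a fraction p of subjects change by m kg before Day 1. Each arm's mean shifts by p × m. The documents give neither value. Assuming p of 10% to 40% and m of 0.5 to 2 kg in size, the shift runs from 0.1 × 0.5 = 0.05 kg to 0.4 × 2 = 0.8 kg. It is the same in all arms in expectation, so the expected shift in the drug-placebo difference is 0.

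**4. Effect on the 7% incidences.** A common shift does not cancel in a difference of tail proportions. Assume percentage change is normal with standard deviation s, mean d on drug and 0 on placebo, plus a common pre-drug shift h. The loss incidence is Φ((-7 - mean - h)/s).

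- s = 4, d = -2.5: with h = 0, drug 13.0%, placebo 4.0%, difference 9.0 points. With h = +0.5, 10.6%, 3.0% and 7.5 points (from unrounded values).
- s = 3, d = -1.5: the difference goes from 2.4 points (h = 0) to 1.7 (h = +0.5).
- The sign of h is unknown. With s = 4, d = -2.5 and h = -0.5, Φ(-1) = 15.9% on drug and Φ(-1.625) = 5.2% on placebo, so the difference rises to 10.7 points.

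With no drug effect the incidences are equal whatever h is, so the CMH test remains valid. What moves is the size of the contrast.

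**5. Effect on precision.** If pre-drug and on-drug changes are independent, the standard deviation grows by √(a² + b²)/a. Assume on-drug a = 2.5 kg. Then b = 0.5 kg gives √6.5/2.5 = 1.02, b = 1.0 gives √7.25/2.5 = 1.08, and b = 1.5 gives √8.5/2.5 = 1.17. That is an increase of 2% to 17% if the pre-drug variation applies to every subject, and less if it applies to only some.

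**The case against.** **Randomization protects the comparison.** The ANCOVA compares arms allocated 1:1:1 after washout and run-in, so pre-drug change is balanced in expectation. This stands in full. A reader might infer that the planned treatment difference in mean weight change is biased. It is not; it is only noisier.

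**The timing is easy to overstate.** A reader might infer that the weight precedes washout by up to five weeks. The documents do not support that. Thirty-five days is the longest gap to the first double-blind dose. The gap to Day -7, when washout must be complete, is at most 28 days. Inclusion criterion 8 asks for willingness to stop prohibited psychotropics from consent, and screening may take more than one visit, so some weights may fall after washout has begun.

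**Regain is not in the documents.** A reader might infer that subjects regain weight after stopping stimulants and so mask drug-related loss. Nothing in the protocol or SAP says that ADHD medication lowers weight or that stopping it raises weight. Only the weight-loss supplements are tied to weight, by their name. Washout concerns only subjects taking such products, and their number is not given.

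**A Visit 3 weight might be intended.** The vital-signs list is open-ended, Appendix 3 includes weight, and Table CT-13.1.1 is planned by study day. But Protocol 7.5.3 names vital signs and body weight separately, and Appendix 3 sets criteria, not visits. If the parenthesis in 3.7.5.3.1 covers BMI alone, there is still no physical examination at Day -1. The ambiguity does not supply a measurement.

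**The stakes are limited.** Appetite and weight complaints are also collected as adverse events at every visit, against placebo. That is true, and this is one safety variable.

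**Conclusion.** The point holds as a mislabelled safety baseline. By schedule, the double-blind baseline weight is the screening weight, 8 to 35 days before Day 1, with 16% to 46% of the screening-to-Day-42 interval falling before any active drug. These figures rest only on the documents' visit days.

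Within-arm weight change and the 7% incidences include washout and run-in change, and the between-arm comparison loses some precision. The mean drug-placebo difference is unbiased in expectation, and the test on the 7% rates remains valid, though the size of that contrast can move either way. All kilogram, percentage-change and standard-deviation figures are assumptions to show scale; the documents give no basis for choosing among them or for a direction. No efficacy analysis is affected. This is a cheap improvement, not a threat to the trial's conclusions.

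**What to change.** Add body weight at Visit 3 (Day -1) to Table 3.7-1 and Protocol 3.7.5.3, and use it as the double-blind baseline in SAP 9.5.1, SAP Appendix 1 and the CT-13 tables. Waist circumference can be taken at the same time. The cost is one scale reading at a visit that already takes place.

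If no Visit 3 weight exists, change the SAP and table titles to change from screening for all subjects, rather than mixing baselines of different ages. Report the interval from that weight to Day 1, and rest conclusions on the between-arm contrast, not on within-arm change. Adjusting the ANCOVA for ADHD or weight-loss medication use at screening is optional. It may recover some precision in the mean comparison but does nothing for the 7% analysis. This route costs SAP wording only.

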3.7.5.3.2 Vital Signs

Vital signs including systolic blood pressure and diastolic blood pressure, heart rate, respiratory rate, and body temperature will be measured at the time points described in the Schedule of Assessments ([Table 3.7-1](#) and [Table 3.7-2](#)). Blood pressure and heart rate measurements will be made in the supine and standing positions after the subject has been in each position for at least 3 minutes. The supine measurements will be performed first followed by the standing measurements. Temperature and respiratory rate will be taken with the subject in the supine position.

Subjects should be monitored for potentially clinically significant vital signs values ([Appendix 3](#)). Abnormal results that are deemed clinically significant should be repeated to ensure reproducibility of the abnormality. Any abnormalities considered by the investigator to be clinically significant are to be recorded as AEs on the AE eCRF ([Section 5.2](#)).

3.7.5.4 Electrocardiogram Assessments

The 12-lead ECGs will be performed in the supine position at the time points described in the Schedule of Assessments ([Table 3.7-1](#)).

Subjects should be monitored for potentially clinically significant ECG results ([Appendix 4](#)). Tests with abnormal results that are deemed clinically significant should be repeated to ensure reproducibility of the abnormality. Any abnormalities considered by the investigator to be clinically significant are to be recorded as AEs on the AE eCRF.

3.7.5.5 Other Safety Assessments

3.7.5.5.1 Study Medication Withdrawal Questionnaire

The SMWQ is a questionnaire to assess withdrawal symptoms that will be completed as described in the Schedule of Assessments ([Table 3.7-1](#) and [Table 3.7-2](#)). The SMWQ is a modification of the Amphetamine Withdrawal Questionnaire in which the terms “amphetamines and methamphetamine” are replaced with the term “the study medication.”^{36,37,38} At the site, the subject will complete the SMWQ, and on non-site days, subjects will complete the SMWQ remotely.

3.7.5.5.2 Columbia-Suicide Severity Rating Scale

Suicidality will be monitored during the trial ([Table 3.7-1](#) and [Table 3.7-2](#)) using the C-SSRS.³⁹ The C-SSRS is a semi-structured interview that captures the occurrence, severity, and frequency of suicide-related thoughts and behaviors during the assessment period.³⁹ The interview includes definitions and suggested questions to solicit the type of information needed to determine if a suicide-related thought or behavior has occurred.

Protocol 405-201-00013

The interview and rating for the C-SSRS must be completed by a licensed clinician who has been successfully trained to rate this scale by the sponsor or a designee, and is medically responsible for the subject. Documentation of trial training should be maintained in the investigational site's files.

The C-SSRS has a "Screening/Baseline" version, which will be completed at screening and a "Since Last Visit" version that will be completed at all other visits (including the ET visit, if applicable). There are a maximum of 19 items to be completed: 7 required, 10 potential additional items if there is a positive response to a required item, and 2 items for suicide/suicide behavior present during the interview. The C-SSRS uses dichotomous scales (ie, yes or no), Likert scales, and text or narrative to further describe the thoughts or behaviors.

3.7.6 Pharmacokinetic and Pharmacogenomic Assessments

All blood collections must occur after the administration of efficacy assessments and safety assessments (eg, AE monitoring, physical examination, vital sign measurements, ECGs, medication withdrawal scales, and suicidality) at any given visit.

3.7.6.1 Pharmacokinetic Assessments

3.7.6.1.1 Pharmacokinetic Blood Samples

Five sparse PK samples will be taken for determination of concentrations of centanafadine and metabolite(s) in plasma. Blood samples will be collected by trial centers that have appropriate facilities. A 2-mL sample will be collected at the time points presented in the Schedule of Assessments ([Table 3.7-1](#)). Samples collected at Day 14 and Day 42/ET should be taken concurrently with the serum chemistry sample. The actual date and time of the PK sample collection must be recorded on the eCRF. The exact timing of sampling relative to previous dose is not critical and can vary as much as is operationally practical. Preferentially, 3 of the 4 PK samples taken during the treatment period per subject should be taken as follows:

- At least 1 sample should be taken prior to the first morning dose (trough concentration) at either Day 7, Day 14, or Day 28
- At least 1 sample should be taken at least 1 hour after the morning dose
- At least 1 sample should be taken after the afternoon dose

All plasma samples will be shipped to the central laboratory. Detailed handling and shipping instructions are in [Appendix 1](#).

Protocol 405-201-00013

3.7.6.2 DNA Blood Samples for Pharmacogenomic Testing

A blood sample will be collected at the time point presented in the Schedule of Assessments ([Table 3.7-1](#)) in order to extract deoxyribonucleic acid (DNA) and determine the genotypes related to drug metabolizing enzymes and transporters to determine the genotypes of genes related to absorption, distribution, metabolism, and excretion. Genotypes and estimated phenotypes may be included as part of a population PK analysis to be reported separately. All samples will be shipped to the central laboratory. Detailed handling and shipping instructions are provided in [Appendix 1](#).

3.7.6.3 Future Biospecimen Research

A blood sample will be collected at the time point presented in the Schedule of Assessments ([Table 3.7-1](#)) only from those subjects that provided consent for FBR sample collection. Research performed on this sample may include genetic analyses (DNA), gene expression profiling (ribonucleic acid [RNA]), proteomics, metabolomics or the measurement of other analytes. Such research is for biomarker testing to address emergent questions not described elsewhere in the protocol (as part of the main trial) and will only be conducted on specimens from appropriately consented subjects. The objective of collecting specimens for future biomedical research is to explore and identify biomarkers that inform the scientific understanding of diseases and their therapeutic treatments. Processing, storage, and shipping instructions for FBR samples are provided in [Appendix 1](#).

3.7.7 End of Trial

The end of trial date is defined as the last date of contact or the date of final contact attempt from the post-treatment follow-up eCRF page for the last subject completing or withdrawing from the trial.

Protocol 405-201-00013

